1.4 Sample Size Justification

The expected mean decline in FACT-P score and within group standard deviation for the control arm treated with 12 months of LHRHa monotherapy are 4-8 and 8-12 points, respectively, based on prior studies of measuring QOL using FACT-P among men treated with ADT [1, 2, 3]. A change in total FACT-P score that is clinically meaningful and impacts treatment in prior studies ranges from 5-8 points depending on cancer subtype [4]. Approximately 30 subjects will be randomized to each of the 3 treatment arms for this comparison. Accounting for a dropout/questionnaire non-completion rate of 10%, this will allow for 27 evaluable subjects per study arm. For the comparison of the mean change in FACT-P score between apalutamide monotherapy and LHRHa monotherapy, this sample size has 80% power to detect an effect size of at least 0.86, corresponding to a difference of 7.5 points in mean 12 month change in FACT-P

score between treatment groups with a common standard deviation for the change in each arm of 8.7 which is similar to the reported standard deviation for LHRHa monotherapy. This is based upon a 2-group t test, using a bi-directional level of significance of 0.025 (adjusted for 2 comparisons). To test for non-inferiority in QOL with apalutamide + LHRHa compared with LHRHa monotherapy, inferior QOL is defined as a greater than 7-point difference in mean change in FACT-P score between the treatment groups and the common standard deviation is again assumed to be 8.7. This sample size has 82% power to reject the null hypothesis of a difference in mean score and accept the alternative hypothesis of non-inferiority with an effect size of at least 0.81, using a 2-group t-test with 2-sided α of 0.025.

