2.2.5 Quality of Life

The FACT-P, EORTC QLQ-C30/QLQ-PR25, and SHIM questionnaires will be completed at the end of Month 3 and Month 12 or at the time of PSA or radiographic progression (if occurs before Month 12, every effort will be made to obtain the 12-month questionnaires for those who discontinue before 12 months).

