5.2.1 Analytic Plan for the Primary Endpoint

Change from baseline in FACT-P total scale will be analyzed using a mixed-model for repeated measures. The model will include baseline scale, treatment, month (categorical), and treatment-by-month interaction as covariates. An unstructured variance-covariance matrix will be used to model within-subject errors, but simpler structures (eg, compound symmetry) may be used to ensure estimation convergence. Change from baseline will be estimated using least-squares means with factor levels weighted according to overall baseline sample means. Data up to 12 months will be included in the analysis and the primary time point of interest will be at 12 months. Contrasts will be set up to compare apalutamide monotherapy vs. LHRHa monotherapy and apalutamide + LHRHa vs. LHRHa monotherapy. To test for non-inferiority with respect to apalutamide + LHRHa compared with LHRHa monotherapy, inferior boundary is defined as a greater than 7-point difference in mean change in FACT-P total score. The estimated least-squares mean (+/- SE) over time will be presented using a line plot. A sensitivity analysis will be conducted by including data up to 24 months.

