5.3.1.3 Metabolic and Hormonal Parameters

The mean change from baseline for markers of insulin resistance (including fasting glucose, insulin, body mass index, and hemoglobin A1C), fasting lipid panel (including total cholesterol, LDL, HDL, and serum triglycerides), and hormone levels (including DHT and estradiol) analyzed using a similar approach as for the primary endpoint.

The mean change in bone mineral density at the femoral neck, and lumbar spine as measured by DEXA scan will be compared for apalutamide monotherapy vs. LHRHa monotherapy and apalutamide + LHRHa vs. LHRHa monotherapy using an analysis of covariance that controls for baseline values of the corresponding measurement.

The time to serum testosterone recovery to > 50 ng/dL and > 150 ng/dL after the cessation of protocol therapy at 12 months will be compared for apalutamide + LHRHa vs. LHRHa monotherapy. The probability distributions by treatment group of the time to testosterone recovery will be estimated using the Kaplan-Meier method. The log-rank test will be used to compare the distribution of time to testosterone recovery. Subjects who discontinue study drug prior to 12 months for disease progression, unacceptable toxicity, or study withdrawal, as well as subjects who continue hormonal therapy after 12 months or receive non-protocol therapy, will not be included in the analysis of this exploratory endpoint.

No adjustment for multiple comparisons will be made for the analysis of the secondary and correlative endpoints.

Table 1: Key censoring rules

Scenario	Censoring rule
Time to PSA Progression	
 Any increase in PSA to $> 50\%$ of the baseline value or an increase of ≥ 2 ng/mL above the nadir, whichever is higher, and confirmed by repeat measurement at least 2 weeks later is considered an event. Subjects who have no PSA progression at the time of analysis will be censored at the last known date of PSA assessment. Subjects without a baseline PSA or without any post baseline values will be censored at randomization date.

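### The FACT-P repeated-measures model has no baseline-by-month term, so one baseline slope serves Month 3 and Month 12; if the true slopes differ, the Month-12 contrasts lose a little precision and some baseline adjustment

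*SAP*

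**What the plan says.** SAP 5.2.1 defines the mean structure of the primary mixed model: "The model will include baseline scale, treatment, month (categorical), and treatment-by-month interaction as covariates". Protocol 11.4.1 gives the same terms, and SAP 5.3.1.1 repeats them for the secondary quality-of-life scales. SAP 5.3.1.3 refers back to the primary method for the metabolic and hormonal markers, with "hormone levels (including DHT and estradiol) analyzed using a similar approach as for the primary endpoint". None of these sections lists a baseline-by-month interaction.

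On the covariance, SAP 5.2.1 says: "An unstructured variance-covariance matrix will be used to model within-subject errors, but simpler structures (eg, compound symmetry) may be used to ensure estimation convergence". On timing it says: "Data up to 12 months will be included in the analysis and the primary time point of interest will be at 12 months". It adds a sensitivity analysis that brings in data to 24 months.

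SAP 2.2.5 fixes the on-therapy visits: the "questionnaires will be completed at the end of Month 3 and Month 12 or at the time of PSA or radiographic progression". The model therefore has two scheduled post-baseline visits.

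The sample size (SAP 1.4) rests on a two-group t test of the 12-month change, "corresponding to a difference of 7.5 points", with a "common standard deviation for the change in each arm of 8.7". It takes no credit for baseline adjustment.

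**The concern.** The plan lets the treatment effect differ by month and, under the unstructured matrix, lets the residual variance differ by month. It does not let the effect of baseline differ by month. The slope of a change score on baseline is (correlation with baseline × SD ratio) − 1. If the correlation with baseline declines between Month 3 and Month 12 while the SDs stay similar, the Month-12 slope is steeper than the Month-3 slope. The fitted slope then lies between the two and under-adjusts Month 12.

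Two things are at stake for the superiority and non-inferiority contrasts: a Month-12 residual variance larger than it need be, and part of any chance baseline difference left in the estimate. With about 30 men per arm, and randomisation stratified on PSADT and age but not on FACT-P, baseline differences of 2 to 3 points are ordinary.

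**Working it through.** **The plan's own figure.** With 27 evaluable per arm, effect size 7.5/8.7 = 0.862 and two-sided α = 0.025, the two-sample t calculation gives 80.2% power. The stated 80% reproduces.

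**Inputs.** From the documents: SD of 12-month change 8.7, 30 randomised and 27 evaluable per arm, visits at Months 3 and 12. Assumed, because the documents do not give them: correlations of baseline with Month 3 (r3) and with Month 12 (r12), correlation between Months 3 and 12 (r312), and SD ratio k = Month-12 SD / baseline SD, with the Month-3 SD equal to the baseline SD.

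**Formulas** (complete data, two visits, unstructured covariance):
- Baseline SD: SDb = 8.7 / √(1 + k² − 2·k·r12)
- Slopes of change on baseline: b3 = r3 − 1; b12 = k·r12 − 1
- Residual terms in units of SDb²: v3 = 1 − r3²; v12 = k²(1 − r12²); c = k(r312 − r3·r12)
- Weight of the Month-3 slope in the common slope: w3 = (v12 − c)/(v3 + v12 − 2c), so b_common = w3·b3 + (1 − w3)·b12
- Excess variance of the Month-12 contrast: (b12 − b_common)²/v12
- Imbalance left in the contrast: (b12 − b_common) × baseline difference
- One-SE baseline difference (27 per arm): SDb·√(2/27)

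**One case in full** (r3 = 0.8, r12 = 0.5, r312 = 0.6, k = 1):
- SDb = 8.7/√1 = 8.7; b3 = −0.20; b12 = −0.50
- v3 = 0.36; v12 = 0.75; c = 0.6 − 0.4 = 0.20
- w3 = 0.55/0.71 = 0.77; b_common = −0.155 − 0.113 = −0.268
- Gap b12 − b_common = −0.232; excess variance 0.232²/0.75 = 7.2%, so the SE is 3.5% larger
- One-SE imbalance 8.7 × 0.272 = 2.4 points, of which 0.232 × 2.4 ≈ 0.55 points stay in the contrast

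**Equal SDs (k = 1).** Power is the plan's superiority calculation with the residual SD in place of 8.7.

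| r3 / r12 / r312 | w3 | SE inflation | Points left per 1-SE imbalance | Power, common slope | Power, own slope |
|---|---|---|---|---|---|
| 0.7 / 0.7 / 0.7 | 0.50 | 0% | 0 | 86.7% | 86.7% |
| 0.7 / 0.6 / 0.7 | 0.61 | 0.3% | 0.16 | 88.6% | 88.8% |
| 0.8 / 0.6 / 0.7 | 0.75 | 1.7% | 0.40 | 87.6% | 88.8% |
| 0.8 / 0.5 / 0.6 | 0.77 | 3.5% | 0.55 | 88.6% | 90.8% |

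**Wider grid.** Eight correlation sets were crossed with k = 0.85, 1.0 and 1.15. The weight w3 runs from 0.25 to 0.85. SE inflation runs from 0 to 5.5%. The imbalance left is at most 0.63 points per one-SE difference of 2.2 to 3.2 points. The largest values come from 0.8/0.5/0.6 with k = 0.85. These are limits of the grid only: raising r312 to 0.75 in the case worked above gives w3 = 0.40/0.41 = 0.98, a gap of −0.293, excess variance 0.293²/0.75 = 11.4% (about 5.6% of the SE) and 0.69 points.

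**Simulation check.** For each scenario, 1,500 trials were simulated with 3 × 30 men and 90% observed at Month 12.

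| r3 / r12 / r312 (k = 1) | SE common | SE own slope | SE unadjusted change | Dependence on baseline difference: common | own |
|---|---|---|---|---|---|
| 0.7 / 0.7 / 0.7 | 2.243 | 2.245 | 2.434 | −0.02 | −0.02 |
| 0.7 / 0.6 / 0.7 | 2.086 | 2.083 | 2.359 | −0.07 | −0.01 |
| 0.8 / 0.6 / 0.7 | 2.215 | 2.179 | 2.437 | −0.15 | 0.01 |
| 0.8 / 0.5 / 0.6 | 2.238 | 2.168 | 2.486 | −0.25 | −0.01 |

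Under no treatment effect, the mean estimates lay between −0.05 and 0.06 for both models, which is within simulation error of zero.

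**The case against.** A common-slope model is a valid prespecified analysis, and the two documents agree on it. Four arguments on its side stand.

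1. A reader might infer that the Month-12 contrast is adjusted mostly with the Month-3 slope. That is not a property of the stated model. It needs correlations and SDs that the documents do not supply. The weight is 0.50 with equal correlations and SDs, where nothing is lost. It is also 0.50 under the compound-symmetry fallback with complete data, and below one half when the Month-12 residual variance is the smaller.
2. The SD ratio matters as much as the correlations. With 0.7 at Month 3 and 0.6 at Month 12, a Month-12 SD about 17% larger equalises the slopes (0.6 × 1.167 = 0.70). With 0.7 at both visits and k = 1.15, the leftover changes sign (+0.18 points).
3. A reader might infer that the primary result is biased or that the power claim fails. Neither follows. Randomisation keeps the estimate unbiased on average, and the leftover is conditional on a chance imbalance that can go either way. The 80% rests on an unadjusted SD of 8.7, and the common-slope model still beats unadjusted change in every simulated scenario.
4. Because SAP 5.3.1.3 borrows the primary method, a reader might infer that the term belongs there too. The laboratory markers have up to six post-baseline visits (Months 3, 6, 9, 12, 18, 24), hence up to five extra slopes. BMI has up to 18 (12 monthly, then 6 two-monthly), hence up to 17, in about 90 men. The bone-density comparison is an ANCOVA and does not have the problem.

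None of this removes the point for FACT-P. When the slopes differ there is a small avoidable loss, and when they do not the extra term costs almost nothing.

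**Conclusion.** The point holds as a minor one. The FACT-P model imposes one baseline slope on Month 3 and Month 12. If the slopes differ, the Month-12 contrasts lose about 0 to 3.5% of their SE with equal visit SDs, and at most about 5.5% over the grid. They also keep 0 to about 0.6 points of a one-SE baseline imbalance, against a 7-point margin and an SE a little above 2. If the slopes are equal there is no loss and no gain.

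The fact that rests on the documents is the absent term. The sizes rest on assumed correlations and SD ratios, on the plan's SD of 8.7, and on treating the data as two scheduled visits without separate handling of progression-visit questionnaires. The documents do not support calling this a threat to the primary result or to the stated 80% power.

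Settling it in advance is still worthwhile. The trial is small and open-label, and adding the term once results are known would be open to question. The 24-month sensitivity analysis also stretches the single slope over a third, off-therapy visit, so the Month-12 estimate could shift slightly for a reason unrelated to what that analysis is meant to test.

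**What to change.** In SAP 5.2.1 and Protocol 11.4.1, make the term list: baseline score, treatment, month, treatment-by-month and baseline-by-month. Use the same list for the secondary quality-of-life models in SAP 5.3.1.1 and for the 24-month sensitivity analysis. Keep estimation of the Month-12 contrasts at the overall baseline mean, as already planned.

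The cost is one phrase, one degree of freedom in the primary model and one more when Month 24 is included. No new data are needed. With equal slopes the simulated SEs are indistinguishable (2.243 and 2.245).

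Do not extend the term automatically to the metabolic and BMI models in SAP 5.3.1.3. If it is wanted there, decide it separately in view of the number of visits. Leave the bone-density ANCOVA as it is.

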5.3 Secondary Endpoints

The following secondary endpoints will be analyzed:

A) Quality of Life:

- Mean change from baseline in total FACT-P score over time
- Mean change from baseline in EORTC QLQ-C30/PR25 score over time
- Mean change from baseline in SHIM score over time

B) PSA Modulation:

- Time to PSA progression, which is defined as a rise to greater than 50% of the baseline serum PSA or rise of 2 ng/mL or more above the nadir, whichever is higher, confirmed by repeat measurement at least 2 weeks later (see Table 1 for the censoring rules).
- Proportion of subjects without evidence of PSA or radiographic progression during the 24-month treatment period and with recovery of serum testosterone at 24 months. Testosterone recovery will be defined as a serum testosterone greater than 150 ng/dL.
- Proportion of subjects with a PSA less than 0.2 ng/mL after 7 months of protocol therapy

C) *Metabolic and Hormonal*

- Mean change from baseline in markers of insulin resistance (including body mass index, fasting glucose/insulin, and hemoglobin A1C), fasting lipid profile, and bone mineral density as measured at the femoral neck, and lumbar spine by DEXA scan over time
- Time to testosterone recovery to greater than 50 ng/dL (non-castrate) and greater than 150 ng/dL during the off-therapy observation period for subjects randomized to the LHRHa-based treatment arms (see Table 1 for the censoring rules)
- The mean change from baseline in serum DHT and estradiol levels over time

5.3.1 Analytic Plan for the Secondary Endpoints

5.3.1.1 Quality of Life

The secondary QOL endpoints will be analyzed using a mixed-model for repeated measures like the primary endpoint. The model will include baseline scale, treatment, month (categorical), and treatment-by-month interaction as covariates. FACT-P, EORTC QLQ-C30/PR25, and SHIM scales are described in sections 5.4.1, 5.4.2, and 5.4.3, respectively.

5.3.1.2 PSA Modulation

The proportion of subjects without PSA or radiographic progression and who have recovered serum testosterone to greater than 150 ng/dL at 24 months from Day 1 will be compared for subjects treated apalutamide monotherapy vs. LHRHa monotherapy and for apalutamide + LHRHa vs. LHRHa monotherapy. The proportions by treatment will be compared using the chi-square test or Fisher's exact test as appropriate and summarized using either risk ratio or risk difference and corresponding 95% confidence interval. Results will be summarized at 24 months from Day 1 with 95% confidence intervals for each treatment arm. Subjects who withdraw from the study prior to 24 months after Day 1 will not be included and this analysis will be conducted as modified intent-to-treat (mITT).

The proportion of subjects with a PSA less than 0.2 ng/mL after 7 months of protocol therapy will be analyzed using similar approaches for proportion of subjects without evidence of PSA or radiographic progression during the 24-month treatment period and with recovery of serum testosterone at 24 months.

The probability distributions by treatment group of the time to PSA progression will be estimated using the Kaplan-Meier method. Durations will be measured from Day 1 of study treatment to the first date of PSA progression. The log-rank test will be used to compare the distribution of time to PSA progression.

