6 STUDY RATIONALE

6.1 RATIONALE FOR THE STUDY POPULATION

Subjects with a PSADT of less than or equal to 12 months will be enrolled in an attempt to include as many subjects as possible while insuring that included subjects remain at sufficiently high risk to warrant ADT. Subjects will be stratified by PSADT of < 6 months vs. 6-12 months, as those with PSADT < 6 months have a shorter time to progression in prior studies [5]. Subjects will be additionally stratified by age (≤ 70 vs. > 70 at the time of study enrollment), as older age is associated with a longer time to testosterone recovery after cessation of ADT. The minimum PSA required for study entry follows commonly used guidelines to define biochemical recurrence while also allowing for accurate measurement of PSADT (greater than 1.0 ng/mL post-RP and nadir + 2 ng/mL post-RT) [43].

Prior ADT used in combination with RT will be permitted, as neoadjuvant, concurrent and adjuvant ADT is the standard of care for high-risk localized prostate cancer patients undergoing definitive radiation therapy. Prior ADT used in the context of RT will be permitted, provided the last effective ADT was > 6 months prior to randomization, and if serum testosterone has recovered to > 150 ng/dL prior to randomization. Due to relatively small sample size per study arm, PSADT and age will be the 2 stratification factors. Nevertheless, prior hormonal therapy will be a demographic variable compared between study arms. Time from definitive therapy to biochemical relapse, as well as Gleason grade at the time of diagnosis are 2 other validated prognostic factors in BCR patients, which will also be measured at baseline and compared between study arms [44, 45].

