7.3.3 Radiographic Studies

Once the subject has given written informed consent and is eligible for the study as per the laboratory/clinical parameters outlined above, the following radiographic information will be collected.

- Radionuclide bone scan

- Cross-sectional imaging of the abdomen and pelvis with IV contrast per investigator discretion (CT or MRI). Subjects who are intolerant of IV CT contrast agents may have CT scans performed with oral contrast or without any contrast, as long as method is identical each time new scans are done.
- DEXA bone densitometry scan with measured bone mineral density at the femoral neck, and lumbar spine (see <https://www.shef.ac.uk/FRAX/tool.aspx?country=9>).

Radionuclide bone scans and CT/MRI images must have been done within 6 weeks prior to randomization. There will be no central reading of the scans and radiographic progression is based on investigator assessment. The DEXA bone densitometry scan must have been taken within 12 weeks prior to randomization.

7.4 RANDOMIZATION:

Once eligibility is confirmed, subjects will be stratified according to their pre-study PSADT (<6 months vs. 6 – 12 months) and age at study entry (≤ 70 vs. > 70). They will be randomized with equal probability to 1 of the 3 treatment arms from within each of the 4 strata. Balance in treatment assignment will be achieved using a randomized block design. Randomization will be carried out via computer generated random assignment. All subjects must commence treatment within (5 calendar days) of randomization. Study sites will email the Eligibility Checklist to the sponsor in order to obtain the subject's treatment assignment. Once subject eligibility is confirmed by the sponsor, an email with the treatment assignment number will be provided to the study site.

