1.5 Randomization and Blinding

1.5.1 Randomization

Upon verification of inclusion and exclusion criteria, eligible patients will be centrally randomized in a 1:1:1 ratio to apalutamide monotherapy, apalutamide + LHRHa, or LHRHa monotherapy. The randomization will be stratified as follows:

- PSADT (< 6 months vs. 6-12 months)
- Age at study entry (≤ 70 years vs. > 70 years)

Balance in treatment assignment will be achieved using a randomized block design. Randomization will be carried out via computer generated random assignment. All subjects must commence treatment within (5 calendar days) of randomization. Study sites will email the Eligibility Checklist to the sponsor to obtain the subject's treatment assignment. Once subject eligibility is confirmed by the sponsor, an email with the treatment assignment number will be provided to the study site.

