5. EFFICACY

This section outlines the planned analyses of the primary, secondary, and other efficacy endpoints of the study.

Efficacy analyses will be performed in the ITT population, incorporating the randomization stratification factors. All continuous variables will be summarized using number of subjects (n), mean, standard deviation (SD), median, minimum, and maximum. Categorical variables will be summarized with count and percentage.

Time-to-event endpoints will be summarized using the Kaplan-Meier method [6] and displayed graphically where appropriate. Median event times and two-sided 95% confidence interval (CI) for each treatment group will be provided. Stratified Cox proportional-hazard models will be used to estimate the hazard ratio (HR) and its 95% CI. The stratification factors to be used in the analysis are PSADT (< 6 months vs. 6-12 months), and age at study entry (≤ 70 years vs. > 70 years).

The testing for the time-to-event endpoints will be based on the stratified log rank test; non-stratified log rank test will be performed as a sensitivity analysis, as appropriate. Multivariate Cox regression analysis, adjusting for important selected prognostic factors.

The proportional hazard assumption will be assessed graphically by plotting log (-log [estimated survival distribution function]) against log (survival time). The resulting graphs should have approximately parallel lines when the assumption holds. If the proportional hazards assumption is reasonably met, then the HR will be used as an estimate of treatment effect. If the proportional hazards assumption is violated, then the inference remains statistically valid for testing equality in survival distributions, but treatment effect will only be estimated using the median time to event in each treatment group.

Endpoints with binary outcome will be summarized by descriptive statistics (count and percentage) by the treatment group. The risk ratio or risk difference (treatment: control) will be reported along with the corresponding two-sided 95% CI. The two treatment groups will be compared by using the chi-square test; Fisher's exact test may be used if the expected counts in some of the cells are less than 5.

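### The SAP's general rule brings the randomisation strata into efficacy analyses, but the tests named for the binary secondary endpoints are unstratified; if the strata are prognostic this costs roughly 1 to 5 points of power

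*SAP*

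**What the plan says.** Randomisation is blocked within four strata: PSA doubling time (PSADT) under 6 versus 6 to 12 months, crossed with age up to 70 versus over 70. Protocol 7.4 says "They will be randomized with equal probability to 1 of the 3 treatment arms from within each of the 4 strata", and SAP 1.5.1 gives the 1:1:1 ratio.

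SAP Section 5 opens with a general rule: "Efficacy analyses will be performed in the ITT population, incorporating the randomization stratification factors". For binary outcomes the same section then says "The two treatment groups will be compared by using the chi-square test; Fisher's exact test may be used if the expected counts" in some cells are below 5. SAP 5.3.1.2 repeats this for the 24-month composite (no PSA or radiographic progression, and testosterone above 150 ng/dL): "The proportions by treatment will be compared using the chi-square test", with Fisher's exact test as the alternative. It sends the proportion with PSA below 0.2 ng/mL after 7 months to the same methods. Protocol 11.4.2 matches. None of these passages names a stratified method.

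For time-to-event endpoints Section 5 is explicit: "The testing for the time-to-event endpoints will be based on the stratified log rank test", with the unstratified version as a sensitivity analysis. SAP 5.3.1.2 and 5.3.1.3 then say only log-rank.

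Protocol 6.1 justifies PSADT as a stratification factor by shorter time to progression, and age "as older age is associated with a longer time to testosterone recovery after cessation of ADT".

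**The concern.** Two things are at issue.

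- **Consistency.** The general rule and the named tests cannot both be followed for the binary endpoints. The trial is open-label, the sponsor runs the analysis, and secondary endpoints carry no multiplicity adjustment, so the main test should be settled before the data are seen.
- **Efficiency.** The two reasons given for stratifying, progression and testosterone recovery, are the two components of the 24-month composite. When allocation is balanced within prognostic strata, the arm difference no longer carries between-stratum variation. The Pearson chi-square still counts that variation in its variance, so it rejects too rarely. With about 30 men per arm there is little power to spare.

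**Working it through.** **Plan's own figures.** No event rate, stratum size or power is given for either binary endpoint. The only power statement that bears on design size is for FACT-P superiority. With 27 per arm, difference 7.5 and SD 8.7, the noncentrality is (7.5/8.7) × √(27/2) = 3.17 on 52 df. At two-sided 0.025 this gives 80.2%, which agrees with the stated 80%.

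**Strength of the strata.** The only figure in the documents is in protocol 1.1: 3-year metastasis risk of 49% (PSADT 0-3 months), 41% (3-6) and 20% (6-12). The odds ratios against 6-12 months are:

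- (0.49/0.51)/(0.20/0.80) = 3.84
- (0.41/0.59)/(0.20/0.80) = 2.78

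The midpoint risk of 45% gives (0.45/0.55)/0.25 = 3.27. This is a proxy from a different endpoint. Nothing quantifies the age effect, so a range is assumed.

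**Why the test is conservative.** Under no treatment effect and exact balance, the variance of the arm difference is proportional to W, the mean of p_k(1−p_k) over strata. Chi-square uses p̄(1−p̄), which is larger whenever the p_k differ. True size is about 2 × [1 − Φ(1.96 / √(W / p̄(1−p̄)))]. Take assumed control rates 0.70/0.45/0.45/0.20 with 9/9/6/6 men per stratum:

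- p̄ = (6.30 + 4.05 + 2.70 + 1.20)/30 = 0.475, so p̄(1−p̄) = 0.2494
- W = (1.89 + 2.2275 + 1.485 + 0.96)/30 = 0.2188
- ratio 0.877; 1.96/√0.877 = 2.09; size about 3.6%

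Simulation of the same case gives 3.7%.

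**Tests compared.**

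- Pearson: (p̂₁ − p̂₂)² / [p̂(1−p̂)(1/n₁ + 1/n₂)].
- Cochran-Mantel-Haenszel (CMH), no continuity correction: [Σ(x_k − S_k m₁k/T_k)]² / Σ[m₁k m₂k S_k(T_k − S_k) / (T_k²(T_k − 1))]. Here x_k is successes in arm 1, S_k is all successes, m₁k and m₂k are the arm sizes and T_k is the total in stratum k.

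**Simulation.** 90 men are randomised 1:1:1 in permuted blocks of 6 within four strata of equal share, with 60,000 runs per scenario at two-sided 0.05. Block size, stratum shares, control rates (30% and 50%), true differences (25 and 33 points) and random exclusion of 0, 10 or 30% are all assumptions. Results with 10% excluded and a 33-point difference:

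| Odds ratio PSADT, age | Size chi-square (control 30% / 50%) | Size CMH | Power chi-square → CMH, control 30% | Control 50% |
|---|---|---|---|---|
| 1, 1 | 5.0% / 5.2% | 4.8% / 5.0% | 69.7 → 68.6% | 75.4 → 74.2% |
| 2, 2 | 4.5% / 4.7% | 4.8% / 5.1% | 70.3 → 71.1% | 75.7 → 76.2% |
| 3.3, 2 | 4.1% / 4.1% | 4.7% / 4.8% | 70.6 → 73.2% | 75.9 → 77.8% |
| 3.3, 3.3 | 4.0% / 3.7% | 4.9% / 4.9% | 70.8 → 74.7% | 76.7 → 79.7% |

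Over odds ratios 2 to 3.3, both differences and 0 to 10% excluded, chi-square size runs from 3.6 to 4.7% and CMH gains 0.5 to 5.3 points. With 30% excluded, CMH loses about 2 points at odds ratios 1, 1, is level or 0.6 points worse at 2, 2, and gains 1 to 2 points at 3.3, 2.

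**Exact tests.** With 30 per arm, exact balance and strata of odds ratio 2 to 3, using Fisher in place of chi-square costs 6 to 8 points. An exact stratified test was simulated with 9/9/6/6 men per stratum and a treatment odds ratio of 4. It gave 56% power against 62% for plain chi-square at the control rates above, and 63% against 71% at weaker ones (0.5/0.35/0.35/0.2).

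**The case against.** **Validity and stakes.** The unstratified test does not inflate type I error. Protocol 6.4.2.3 calls both binary endpoints exploratory. At 27 to 30 per arm, chi-square needs a difference of about 34 to 37 points for 80% power, so these comparisons are weak either way. All of this stands and keeps the point modest.

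**Strength of the strata.** The gain depends on a prognostic strength that the documents do not give for these endpoints. A reader might infer that the planned test certainly loses power, or loses a lot. Control rates of 0.8/0.5/0.4/0.1 do give a size of about 2.5% and power of 47% against 60%. Those rates imply odds ratios of 4 to 9 per factor and 36 between the extreme strata, well beyond the 2.8 to 3.8 proxy. The documents do not support that size, nor an unconditional loss.

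**Scope.** A reader might also extend the efficiency argument to both binary endpoints. Protocol 6.1 links the strata to progression and testosterone recovery, not to PSA below 0.2 ng/mL at 7 months. Even for the composite, the age link is weaker in the monotherapy comparison: protocol 1.3.3 says androgen-receptor antagonist monotherapy does not bring testosterone to castrate levels. Age would then act mainly in the LHRH agonist control arm.

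**Log-rank.** A reader might take the bare log-rank wording in 5.3.1.2 and 5.3.1.3 as a second unstratified plan. Section 5 already makes the stratified log-rank the main test, so only the wording needs aligning.

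**Another remedy.** Limiting the Section 5 sentence to time-to-event endpoints would also remove the conflict. It would, however, set aside strata that the protocol chose for reasons that match the composite.

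**Conclusion.** The inconsistency is real and can be read directly from the SAP. Its statistical cost is conditional and small. If PSADT and age are prognostic for the 24-month composite at odds ratios of about 2 to 3.3, and up to 10% of men are excluded at random, the chi-square test has true size of about 3.6 to 4.7% and gives up roughly 1 to 5 points of power. If the strata carry no information, the stratified test costs about 1 point, or about 2 points with 30% excluded. The PSADT strength is a proxy; the age strength, event rates, stratum shares and block size are assumed. For PSA below 0.2 ng/mL at 7 months only the SAP's own general rule supports the change. Falling back on Fisher would cost more than leaving out the strata.

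**What to change.** In SAP Section 5, SAP 5.3.1.2 and protocol 11.4.2:

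- Make the asymptotic CMH test, stratified by PSADT (<6 vs 6-12 months) and age (≤70 vs >70) and without continuity correction, the main test for both binary endpoints.
- Report the Mantel-Haenszel risk difference with its 95% CI. This also settles the SAP's open choice between risk ratio and risk difference.
- Keep chi-square and Fisher as sensitivity analyses.
- Do not default to an exact stratified test when counts are small. CMH pools over strata, and the exact version can be conservative enough to lose the gain.
- In SAP 5.3.1.2 and 5.3.1.3, write stratified log-rank to match Section 5.

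The cost is a change of wording and a small change in code. The downside is a power loss of about 1 to 2 points if the strata prove not to be prognostic.
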